Official Title:	A Pilot Randomized Trial of Video-based Family Therapy for Depressed Home Visited Mothers
NCT number:	NCT04741776
Document Type:	Protocol and Statistical Analysis Plan
Date of the Document:	10/08/2020

Study Protocol

Study Purpose: Assess the feasibility, acceptability, tolerability, safety, and preliminary effectiveness of a video-based family therapy intervention (Resilience Enhancement Skills Training, REST) in home visited mothers (pregnant and postpartum) with moderate to severe depressive symptoms and moderate to high family conflict.

Study Design: Effectiveness-implementation hybrid type 1 design with a pilot randomized trial.

Sample Size: We aimed to enroll 80 home visited mothers and their family members (N=160) in the study.

Characteristics of Subject Population: Mothers, at least 15 years old, in any trimester of pregnancy through 18 months postpartum, enrolled in participating home visiting (HV) agencies with moderate to severe depressive symptoms on the Beck Depression Inventory-Second Edition [BDI-II] scores of ≥ 20 and moderate to high family conflict with their family members on the Perceived Hostility Survey (Ages 18+) raw scores of at least 16 or Perceived Hostility Survey (Ages 8-17) raw scores of at least 14. *Family member* is defined as the mother's adult relative or her current intimate partner with whom she either lives with in the same home or has at least weekly contact. *Family* is defined as a dyad that includes the mother and her family member.

Scheme. The mother was the unit of randomization in the study. Block randomization with block size of 4 using R package “Blockrand” was used to randomize the mothers to the study groups. Mothers were randomized with equal probability to one of two study groups: 1) video-based family therapy (Resilience Enhancement Skills Training, REST), or 2) the active comparison condition standard of care (Video-delivered individual Problem Solving Therapy, V-PST). The family received REST. Although only the mother received V-PST, the mother and her family member were asked to complete outcome measures.

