Process and blinding. The Statistician used Blockrand to randomize the mothers, by unique study IDs, to the study groups. The PI communicated with Statistician to obtain the study group assignments by unique study ID. The PI called the therapist and family to communicate the study group assignment on the same day the mother and her family member completed the baseline interview. The Research Assistants remained blind to study group assignment, and study participants (mothers and their family members) were instructed by the PI not to discuss their study group assignment with the Research Assistant who administered the study questionnaires to them. In addition, the PI instructed the Research Assistants to remind each study participant not to disclose the study group assignment prior to administering each study questionnaire. Research assistants were regularly supervised by the PI.

Outcomes: The primary outcomes included maternal depressive symptoms (measured using the Beck Depression Inventory-Second Edition), family conflict (measured using the Perceived Hostility Survey Ages 18+ and Ages 8-17 years old), and family cohesion (measured using the Multidimensional Scale of Perceived Social Support – Family subscale). The secondary outcome included maternal job attainment/school enrollment measured using an adapted ABCD study item. Outcomes were assessed from baseline through post-intervention (within one week of the final therapy session), three months later, and six months later.

Monitoring Trial Performance. The PI developed and utilized structured processes for ensuring intervention fidelity and fidelity to the study protocol. For this study, the PI 1) developed initial trainings and refresher trainings for data collection procedures and adherence to safety protocols for research staff; 2) supervised the research staff to ensure adherence to recruitment, data collection, and retention procedures; 3) held weekly meetings with lead staff at participating home visiting agencies to discuss recruitment, home visitor study responsibilities, and any issues related to reallocation of home visitor study responsibilities due to home visitor turnover. In addition, the study included data entry software that minimized missing data by flagging missed items before questionnaires were submitted. The secure, password protected database was regularly maintained and monitored throughout the study.

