Fidelity monitoring for the interventions occurred in two phases. In phase one, the PI and Problem Solving Therapy (PST) expert assessed fidelity on a weekly basis in all 10 audio-recorded sessions for the first 2 families who are assigned to each REST therapist. They continued to assess fidelity on a weekly basis in all 10 audio-recorded sessions for the first two mothers who were assigned to each V-PST therapist. The PI and PST expert discussed and resolved any discrepancies in these fidelity assessments. The PI immediately provided any corrective feedback to REST therapists in weekly supervision. For the V-PST therapists, the PI immediately communicated any corrective feedback to the V-PST supervisor to address with the therapists in weekly supervision.

In phase two, the PST expert assessed fidelity in 10% of randomly selected audio-recorded REST sessions, originally assessed by the PI, and 10% of randomly selected audio-recorded V-PST sessions, originally assessed by the PI. The PST expert and the PI discussed and resolved any discrepancies in the fidelity assessments throughout Years 1 and 2 of the proposed study. These fidelity assessments occurred on an ongoing basis in order to provide immediate corrective feedback to REST therapists and V-PST therapists to ensure high fidelity.

Data and Safety Monitoring Board Procedures (DSMB). The DSMB has established procedures of operation and guidelines for determining the methods and frequency for review of Departmental studies. Table 1, below, guides the risk assessment for the study. Based on the DSMB's established guidelines, the study's total score of 6 on the 10-point scoring system indicates that it poses greater than minimal risk to human subjects. Tasks related to participant safety included the PI's assessment of potential risks associated with study recruitment and participation, and the design and implementation of procedures to minimize these risks should they arise. According to the Departmental DSMB policy, studies in this risk category will be independently monitored by a group of knowledgeable faculty members and an independent statistician. The DSMB met twice per year to monitor the study, which included data analysis by the independent statistician.

Table 1. Study Risk Assessment *					ENTE R SCOR E
I. Experimental Treatment					
Low Risk	No experimental treatment in study	1 point			
Moderate Risk	Treatment effects documented from studies with similar and/or	2 points			2

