Details on the family recruitment procedures, consent procedures, safety monitoring procedures, and the results on feasibility, acceptability, safety and tolerability have been published (please see Cluxton-Keller F, Hegel MT. A video-delivered family therapeutic intervention for perinatal women with clinically significant depressive symptoms and family conflict: Indicators of feasibility and acceptability. JMIR Form Res. 2022;6(10):e41697. doi: 10.2196/41697. PMID: 36194458; and Cluxton-Keller F, Hegel MT, Donnelly CL, Bruce ML. Video-delivered family therapy for perinatal women with depressive symptoms and family conflict: Feasibility, acceptability, safety, and tolerability results from a pilot randomized trial. JMIR Form Res. 2023;7:e51824. doi: 10.2196/51824. PMID: 37921846).

Statistical Analysis Plan

Generalized linear mixed-effects models (GLMM) were used to analyze changes in mothers and family members, separately, with fixed effects for time (baseline, post-intervention, three-month, six-month follow-up), study group (Resilience Enhancement Skills Training, Standard of Care), and study group*time interaction. An intervention effect is indicated by a significant study group*time interaction with greater improvement in the Resilience Enhancement Skills Training group. Individual-level random intercept and slope terms were included to account for correlations from repeated measures. Significance of change from baseline to the six month follow-up was tested for mothers and family members, separately. GLMM was used that accommodates intermittent missing data and attrition, and estimate is not biased assuming missing data mechanism is missing at random (MAR) [1]. The distinction between MAR and missing not at random is not verifiable using observed data [2]. However, we did not empirically observe systematic patterns of missing in the data for this study. While MAR is a plausible assumption in many cases, minor departures from MAR typically do not invalidate the results of an MAR-based analysis. [3-4].

References

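### Does timing the follow-up visits from the last therapy session distort the comparison between arms?

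*Combined protocol and SAP*

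**What the plan says.** The Outcomes paragraph of the protocol sets the visits: "Outcomes were assessed from baseline through post-intervention (within one week of the final therapy session), three months later, and six months later". The natural reading is that the three- and six-month visits count from the post-intervention visit. On any reading the chain starts at the final session.

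The fidelity paragraphs under Monitoring Trial Performance give the same number of sessions in both arms. Fidelity was assessed "on a weekly basis in all 10 audio-recorded sessions for the first 2 families who are assigned to each REST therapist" and, for the comparator, "on a weekly basis in all 10 audio-recorded sessions for the first two mothers who were assigned to each V-PST therapist". Both arms also had weekly supervision. Session spacing and a maximum course length are not stated.

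Under Scheme, REST goes to the dyad and V-PST to the mother alone: "Although only the mother received V-PST, the mother and her family member were asked to complete outcome measures".

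The Statistical Analysis Plan names "fixed effects for time (baseline, post-intervention, three-month, six-month follow-up), study group" and their interaction, with individual random intercepts and slopes. It then specifies the test: "Significance of change from baseline to the six month follow-up was tested for mothers and family members, separately". Missing data are covered by the missing-at-random assumption. Neither part of the document says when visits fall for a mother who stops early or has no session.

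**The concern.** The anchor is an event after randomisation that depends on adherence. Two mothers with the same visit label may be at different distances from baseline, and a mother with no session has no anchor. REST involves two people and V-PST one, so pace or stopping could differ by arm.

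Mothers enter with a BDI-II of at least 20 and raised hostility scores, in pregnancy or up to 18 months postpartum. Scores could well move over time without any therapy effect. If one arm is measured later on average, it has had more time to drift, and the interaction would count that as an intervention effect. Slower REST courses would favour REST if the drift is improvement, and more early stopping in REST would work against it. Because time is described by four visit names, nothing in the plan shows that the model would notice.

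**Working it through.** The documents state no figure on visit timing, so there is none to reproduce. They give no SD, drift rate, session spacing or significance level either. The check asks how large the problem could be.

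**Inputs from the documents:** 80 mothers randomised with equal probability, so about 40 per arm; 10 sessions in each arm; post-intervention visit within one week of the final session; follow-up three and six months later.

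**Assumptions:** first session one week after baseline; weekly sessions; six months = 26 weeks, counted from the post-intervention visit; one month = 4.345 weeks; SD of change 8.3 to 10 BDI-II points; the same linear drift of 1 point a month in both arms (range 0.5 to 1.5); two-sided 5% test.

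**1. Spread within a visit label.**
- Ten weekly sessions: final session at week 10, post-intervention visit at weeks 10–11, six-month visit at weeks 36–37.
- Stopping after session 3, if assessed from that session: weeks 3–4 and 29–30.
- Difference: 7 weeks.

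**2. Gap between arms.** A spread shared by both arms gives no bias of this kind; only a difference in mean elapsed time does. If 30% stop after session 3 in one arm and 10% in the other, the gap is (0.30 − 0.10) × 7 = 1.4 weeks.

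**3. Bias and false-positive rate.**
- Bias b = monthly drift × gap / 4.345.
- SE = SD × √(2/40), which is 1.86 for SD 8.3 and 2.24 for SD 10.
- False-positive rate = Φ(b/SE − 1.96) + Φ(−b/SE − 1.96).

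At a drift of 1 point a month:

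| Gap (weeks) | Bias (points) | Rate, SD 8.3 | Rate, SD 10 |
|---|---|---|---|
| 0 | 0 | 5.0% | 5.0% |
| 1 | 0.23 | 5.2% | 5.1% |
| 1.4 | 0.32 | 5.3% | 5.2% |
| 2 | 0.46 | 5.7% | 5.5% |
| 4 | 0.92 | 7.9% | 7.0% |

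At a 4-week gap, a drift of 0.5 gives 0.46 points (5.7% and 5.5%), and a drift of 1.5 gives 1.38 points (11.5% and 9.5%).

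**4. What a 4-week gap would take.** Through early stopping alone, the arms would have to differ by 4/7 = 57 percentage points in the share stopping after session 3. Through pace alone, the mean course in one arm would have to run about 14 weeks against 10. No passage points to either.

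**5. Direction.** If needing two people both slowed REST and led more REST mothers to stop early, the two effects would partly cancel. If the 1.4-week gap arises from more stopping in REST and drift is improvement, the bias is against REST. The chance of a false finding in favour of REST is then Φ(−1.96 − b/SE): Φ(−2.13) = 1.6% for SD 8.3 and Φ(−2.10) = 1.8% for SD 10, both below the nominal 2.5%.

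**6. The tested contrast.** The plan tests change from baseline to six months, at about weeks 30–37. The table applies there only if drift is still running at the same rate. If it has levelled off, a few weeks either way make little difference and b tends to 0.

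**The case for a change.** The case for a change is sound on structure. The anchor is affected by treatment, the rule for early stoppers and non-starters is absent, and missing at random does not say when a visit is due. The publications that the document cites for feasibility results are not said to cover visit scheduling. Harsher assumptions also give large effects. If one arm ran weekly and the other every two weeks, the gap would be 9 weeks (final session at week 19 against week 10). With a drift of 2 points a month the bias would be 4.1 points and the false-positive rate 46% at SD 10 (64% at SD 8, 34% at SD 12).

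What stands is the omission: a reader cannot tell how early stoppers and non-starters were scheduled. The extreme case does not stand as evidence. It needs every course in one arm at half the pace of the other, despite weekly review and supervision in both, and a steep drift that persists past six months. That two people are involved in REST makes an arm difference possible, but no passage says a session is postponed when one is absent.

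The criticism of the model is also firmer than the text allows. A random slope needs a numeric time variable, and the plan does not say whether that is nominal or actual time.

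The remedies are not clear gains. A model in actual time needs a functional form, and improvement during therapy followed by a plateau is not linear. Its time variable is driven by adherence, so early visits belong to early stoppers. An estimate at 36 weeks would extrapolate for anyone last seen at weeks 29–30. Fixed visits from randomisation would remove the dependence on pace, but some participants would still be in therapy at the first visit, so status at the end of the course would be lost.

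**Conclusion.** No change to the plan is needed. Measuring at the end of therapy and then three and six months on is a reasonable choice for a pilot of feasibility and preliminary effectiveness, and moving the anchor exchanges one question for another. The missing scheduling rule is a detail that the trial team can supply when reporting, with time from randomisation to each visit by arm if dates were recorded. A model in actual time would be exploratory at most.

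The possible bias is zero if pace and stopping are alike in the two arms. For gaps of 1 to 2 weeks it is about 0.2 to 0.5 BDI-II points, and the one scenario built on a specific mechanism raises the false-positive rate from 5.0% to 5.2–5.3%. These sizes rest on assumed drift, SD and gaps, so they show scale only. They would be wrong if the arms in fact differed in timing by a month or more while scores were still drifting at six months. The documents neither show this nor rule it out.

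### Does the SAP leave open which part of the four-visit group-by-time interaction decides an intervention effect?

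*Combined protocol and SAP*

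**What the plan says.** The rule sits in the Statistical Analysis Plan: "An intervention effect is indicated by a significant study group*time interaction with greater improvement in the Resilience Enhancement Skills Training group". The model behind it is a generalized linear mixed model, fitted separately to mothers and to family members, "with fixed effects for time (baseline, post-intervention, three-month, six-month follow-up", together with study group and their interaction. On the covariance it says: "Individual-level random intercept and slope terms were included to account for correlations from repeated measures". Two sentences after the rule comes: "Significance of change from baseline to the six month follow-up was tested for mothers and family members, separately".

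The Outcomes paragraph lists three primary outcomes of equal standing, starting with depressive symptoms and family conflict, with family cohesion as the third. It gives the schedule: "Outcomes were assessed from baseline through post-intervention (within one week of the final therapy session), three months later, and six months later". It names no primary visit. Neither part of the document states a significance level, a power or an effect size. The Study Purpose gives the aim: "Assess the feasibility, acceptability, tolerability, safety, and preliminary effectiveness of a video-based family therapy intervention".

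**The concern.** With time as a four-level factor and two groups, the interaction has (4 - 1) x (2 - 1) = 3 degrees of freedom. A joint test on 3 df has no sign, so greater improvement under REST has to be judged at some visit, and the rule does not say which. Two nearby sentences seem to offer other readings. A random slope could suggest time as a number, which would give a single slope difference. The six-month sentence could be a between-group contrast that decides, or a change tested without comparing groups.

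If the readings are equally open, the same data can yield an effect under one and none under another, on a primary outcome. If whichever test is significant may be cited, the false-positive rate rises too. The SAP also describes the missing data actually seen ("However, we did not empirically observe systematic patterns of missing in the data for this study"), so this text cannot show that the reading was fixed before the data were available.

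**Working it through.** **Inputs.** From the document: 80 mothers, equal allocation, hence 80 / 2 = 40 per arm; four visits; three primary outcomes. Assumed, because the document gives none: two-sided 0.05; complete data; six-month power of 50% or 80%; visits coded 0-3; and either compound symmetry with correlation 0.5 (CS) or a random intercept and slope (RIS: intercept variance 0.5, slope variance 0.05, residual 0.4). There is no design figure in the plan to reproduce.

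**Step 1: how often two readings differ.** Reading A: joint 3-df p < 0.05 and REST ahead at six months. Reading B: six-month group contrast with z > 1.96. Large-sample simulation, 1,000,000 draws, share of trials significant under one reading only (CS / RIS):

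| True effect | 80% power | 50% power |
|---|---|---|
| Constant over follow-up | 14.5% / 15.4% | 21.9% / 24.1% |
| Growing (1/3, 2/3, 1) | 16.4% / 17.0% | 20.8% / 20.9% |
| Fading (1, 0.5, 0), post-intervention power 80% | 37.4% / 38.6% | - |
| None | 3.1% / 3.1% (no power set) | - |

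With 40 per arm and Hotelling and t tests, the constant-effect figures are 15.8% / 16.6% at 80% and 22.1% / 25.2% at 50%. At 90% power, disagreement falls to about 10%. Other correlations and lasting shapes give about 12-32%. These are differences in significance, not effects in opposite directions.

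**Step 2: error rate of the ordinary reading.** With no effect, the joint test rejects 5% of the time and, by symmetry, REST is ahead at any one named visit in half of those: 0.05 / 2 = 2.5%. Reading B also gives 2.5%. However direction is judged, the rate cannot exceed 5% for one outcome, because a significant joint test is still required.

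**Step 3: what an either-test licence would cost.** For one outcome, the readings sum to 0.025 + 0.025 = 0.050 and disagree in 0.031. Both are positive in (0.050 - 0.031) / 2 = 0.0095, and at least one in 0.0095 + 0.031 = 0.0405. For three independent outcomes, reading B alone gives 1 - 0.975^3 = 7.3%. Either test gives 1 - 0.9595^3 = 11.7% (11.8% by simulation). The step from 2.5% to 7.3% comes from having three unadjusted outcomes, which is a separate matter. Only the step from 7.3% to about 11.8% comes from the choice of test, and no sentence in the SAP permits citing whichever test succeeds.

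**Step 4: power under each reading.** Under CS the covariance of the three between-group differences in change is proportional to I + J (J is the matrix of ones), with inverse I - J/4. Up to a common factor, the non-centrality for effect d times shape v is d^2 (v'v - (sum v)^2 / 4) for the joint test and d^2 / 2 for one visit at full effect. For 80% power the latter is (1.96 + 0.84)^2, about 7.85.

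- Constant: (3 - 9/4) / 0.5 = 1.5, so 1.5 x 7.85 = 11.8 and joint power is about 83%, against 80% at six months. RIS gives 90%.
- Growing: (14/9 - 4/4) / 0.5 = 1.11, so 8.72 and joint power is about 70%, against 80%. RIS gives 68%.
- Fading: (1.25 - 2.25/4) / 0.5 = 1.375, so 10.8 and the joint test rejects about 80% of the time. Requiring REST to be ahead at six months, where the true difference is nil, leaves 40% (RIS 41%), against 2.5% for the six-month contrast.

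**Step 5: the sentences side by side.** The fixed effect of time is spelled out as four visits, which is how a factor is described. The random slope is introduced only to handle correlation, and a numeric random slope can stand beside a categorical fixed effect. So a linear-slope interaction has little support in the text. The six-month sentence follows the rule, does not mention study group and is not tied to the declaration of an effect. What remains is the joint test plus a direction check, and the end of follow-up is the natural place for that check.

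**The case for a change.** The strongest case for a change is that an ordinary reading is not a written one. The splits go both ways: under CS with a constant effect at 80% power, 8.9% of trials are positive only on the joint test and 5.7% only at six months, so an unstated choice can help or hurt REST. Preliminary effectiveness is a stated aim, this is the only rule that decides it, and the document was completed after data were seen. Naming one contrast would need no new data and at most one refit per outcome.

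Part of this stands. The figures reproduce. The level is unstated, the visit that sets direction is unnamed, and the six-month sentence does not say whether groups are compared. For a fading effect the direction visit matters, as the gap between 80% and 40% in Step 4 shows.

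The remedy does not follow. It would demote the only test that the SAP links to an effect and promote a contrast that the SAP does not link to it. By Step 4, that gains power for one effect shape and loses it for two. The timing point also cuts both ways: a deciding contrast imposed now would itself be chosen after the data. Effectiveness is one of five aims in a pilot, and the document contains no rule for going on to a larger trial that would turn on this verdict.

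**Conclusion.** No change to the plan is called for. The rule reads most naturally as the joint 3-df interaction test with REST ahead, and so read it holds a 2.5% REST-favouring error rate per outcome when direction is taken at a single visit. The 15-25% disagreement with a six-month contrast is real under the stated assumptions (two-sided 0.05, 50-80% power, lasting effect, one outcome). It measures how far two reasonable tests differ, not an error in the one the plan names. Putting the six-month contrast in its place is a trade-off on which statisticians would fairly differ. The significance level and the direction visit are details that analysts supply by convention, and between-group estimates at all three follow-ups with confidence intervals would let any reader see the pattern over time. This conclusion rests on reading the listed visits as a factor. A dated earlier record showing that time was coded as linear, or that another contrast decided, would reopen the question. Multiplicity across the three primary outcomes is not settled here.
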